9.4.2. Safety Analyses

All DLT assessments will be performed on the DLT-evaluable population (see [Section 8.4](#) for DLT assessment details). All other safety analyses will be performed on the Treated Population. Safety analyses will be descriptive in nature, and will include analyses of DLTs, AEs, SAEs, AEs leading to study treatment discontinuation and/or dose modification, clinical laboratory tests, vital signs, and ECGs. AEs will be coded using Medical Dictionary for Regulatory Activities (MedDRA) coding dictionary. Unless otherwise specified, AEs will be summarized by primary MedDRA system organ classes and Preferred Term. Safety analyses will be summarized by the initial combination dose level. Safety analyses will be presented for each cohort separately and for the overall study population.

During dose expansion after the final expansion dose has been selected, evaluation of all Grade 4 or higher treatment-related adverse event rates will be conducted to assess if the unacceptable toxicity threshold has been reached. If this threshold is met, enrollment to dose expansion will be halted pending review of safety data. After reviewing the totality of data from both CodeBreaK 101C and cumulative data from this study, one of the following actions may be taken:

1. Terminate the study
2. Amend the protocol to potentially improve the benefit/risk for subjects (eg, increase safety monitoring, modify dose/schedule, mandate premedication)
3. Continue dose expansion without any changes

The stopping rules use a Bayesian approach to pause the enrollment if the posterior probability is $\geq 80\%$ that the Grade 4 or higher treatment-related adverse event rate is greater than 20%. The stopping boundaries shown in [Table 9](#) assume a prior distribution of Beta (0.4, 1.6). The operating characteristics with the pre-specified batch size of 10 new subjects are summarized in [Table 10](#).

Table 9: Stopping Boundary by Number of Subjects

Number of Subjects Treated	Number of Subjects with Grade 4 or Higher Treatment-Related Adverse Events to Halt Enrollment
10	≥ 4
20	≥ 6
30	≥ 9
40	Expansion complete

Table 10: Operating Characteristics of Stopping Rules

True Grade 4 or Higher Treatment-Related Adverse Event Rate	Probability of Early Stopping of Dose Expansion	Average Dose Expansion Sample Size
0.1	2.1%	39
0.15	9.7%	38
0.2	25.8%	34
0.25	47.7%	29
0.3	69.2%	23

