8.3.6. Committees

8.3.6.1. Dose Committee

The Dose Committee is a study specific committee, composed of Sponsor representatives and investigators. Additional details regarding memberships, roles, and responsibilities are provided in the Dose Committee Charter.

The Dose Committee will evaluate the safety data for the safety lead-in portion of the study. The combination dose for the expansion phase of the study will be decided by the Sponsor after taking into consideration the totality of data from both CodeBreaK 101C and the cumulative data from this study. The Sponsor may proceed directly to dose expansion in this study without completing the safety run-in period based on review of available data.

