APPENDIX 11. MODIFIED TOXICITY PROBABILITY INTERVAL-2 (mTPI-2) DESIGN DETAILS

Dose escalation/de-escalation during the safety run-in phase will follow an mTPI-2 algorithm (Guo, 2017), with a target dose-limiting toxicity (DLT) probability of 0.30 and the acceptable toxicity probability interval of 0.25 to 0.35.

DLT assessment will be performed on the DLT-evaluable population (see [Section 9.3](#)), as guided by the following mTPI-2 decision table.

		Dose Escalation Rule of the Modified Toxicity Probability Interval-2 Method						
		Number of DLT-Evaluable Subjects Treated at Current Dose						
		3	4	5	6	7	8	9
Number of Dose-Limiting Toxicities	0	E	E	E	E	E	E	E
	1	S	S	E	E	E	E	E
	2	D	D	D	S	S	S	E
	3	DU	DU	D	D	D	D	S
	4		DU	DU	DU	D	D	D
	5			DU	DU	DU	DU	DU
	6				DU	DU	DU	DU
	7					DU	DU	DU
	8						DU	DU
	9							DU

Source: Guo W, Wang SJ, Yang S, et al. A Bayesian interval dose-finding design addressing Ockham's razor: mTPI-2. *Contemp Clin Trials*. 2017;58:23-33.

Abbreviations: D = de-escalate to the next-lower dose; DLT = dose-limiting toxicity; DU = de-escalate to the next-lower dose and the current dose will never be used again because of unacceptable high toxicity (ie, the probability that the DLT rate is higher than 30% at the current dose is greater than 95%); E = escalate to the next-higher dose; S = stay at the current dose.

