2.3 Sample Size Determination

Up to a total of 46 subjects will be enrolled into this study. Approximately 6 to 12 subjects will be enrolled during the safety run-in portion of the study. Initially, up to 6 subjects will be enrolled and treated at the dose of 140 mg BIW on D1D2 of each week in a 21-day cycle (i.e., Days 1, 2, 8, 9, 15, and 16 of each 21-day cycle) in combination with sotorasib at 960 mg QD. An additional 6 subjects may be enrolled to receive RMC-4630 200 mg BIW on D1D2 of each week in a 21-day cycle (i.e., Days 1, 2, 8, 9, 15, and 16 of each 21-day cycle) in combination with sotorasib at 960 mg QD, if a decision is made to increase the RMC-4630 dose from 140 mg to 200 mg. After completion of the safety run-in (DLT clearance) of both dose levels, additional patients may be enrolled for the purpose of dose optimization to inform the selection of the final expansion dose. Expansion may commence as soon as the final expansion dose has been selected. Approximately 34 to 40 subjects will be enrolled for dose optimization and dose expansion.

With a total sample size of 46 subjects, the probability of observing at least 1 AE with an incidence rate of 5% is at least 90%.

The ORR will be reported by dose level pooling subjects from safety run-in and dose optimization (if applicable) and expansion. It's anticipated that approximately 20 to 40 subjects will be treated at the final expansion dose depending on the actual number of subjects enrolled during safety run-in and/or dose optimization. For the final expansion dose, with 20 and 40 subjects, the lower bound of the one-sided 80% exact CI will be above 33.7% and 37.3% respectively if the observed response rate is 45%.

The mutational status of each subject and, thus, placement into Cohort 1 or 2 (Protocol Section 4.1) will be determined based on the historic genomic reports and later might be adjusted based on ctDNA analysis results collected at baseline. Therefore, the sample size for one or both cohorts will depend on the distribution of mutational status.

3. Endpoints

Primary Endpoints

- ORR as assessed per RECIST v1.1

Secondary Endpoints

- Incidence, nature, and severity of TEAEs, SAEs, clinically significant changes in laboratory tests, ECGs, and vital signs
- Trough and approximate peak concentrations of RMC-4630 and sotorasib
- DOR, DCR, and PFS as assessed per RECIST v1.1, and OS

Exploratory Endpoints

- Sotorasib and RMC-4630 exposure/safety and exposure/efficacy relationships

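### The toxicity pause rule should also cover the optional dose-optimization part, for which the protocol and SAP state no numeric boundary

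*Protocol*

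**What the plan says.** Subjects can be enrolled in three parts, and the plan has two numeric toxicity rules.

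- **Run-in.** Protocol Appendix 11: "Dose escalation/de-escalation during the safety run-in phase will follow an mTPI-2 algorithm". Its table covers 3 to 9 DLT-evaluable subjects at a dose, and Protocol 8.4 counts DLTs in the first cycle only. SAP section 5 limits the DLT-evaluable population to the lead-in. (Protocol Table 8 does not state that limit, but Appendix 11 confines the rule to the run-in.) Protocol 8.3.6.1 adds: "The Dose Committee will evaluate the safety data for the safety lead-in portion of the study".
- **Dose optimization.** Once both levels have cleared the run-in, SAP 2.3 says "additional patients may be enrolled for the purpose of dose optimization to inform the selection of the final expansion dose". Protocol 4.1 allows this at one or both levels, before the final dose is chosen.
- **Expansion.** Protocol 9.4.2 and SAP 7.7 place the Grade 4+ rule "During dose expansion after the final expansion dose has been selected, evaluation of all Grade 4 or higher treatment-related adverse event rates". Crossing it halts enrollment to expansion only.

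The rule pauses when the posterior probability that the rate exceeds 20% is at least 80%, under a Beta(0.4, 1.6) prior. Protocol Table 9 (SAP 7.7 Table 1) gives boundaries of 4/10, 6/20 and 9/30. Protocol Table 10 (SAP 7.7 Table 2) gives operating characteristics for an expansion that completes at 40.

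**The concern.** Optimization begins after the first rule has ended and finishes before the second begins. No count of Grade 4 or higher related events in that part triggers a pause under either document, although the sponsor thought such a pause worth having once the dose is settled. This is the part in which two combination levels may be enrolled while the choice between them is open.

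Clearing the run-in is not a substitute. It rests on up to 6 subjects per level and on Cycle 1 events, whereas Protocol 2.2.2.3 expects that combination toxicity may grow with time on treatment. An excess appearing in later cycles is what the Grade 4+ rule can detect and a Cycle 1 DLT count cannot.

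**Working it through.** **1. Reproduce the plan's own rule.** With r events in n subjects the posterior is Beta(0.4 + r, 1.6 + n − r). The boundary is the smallest r with P(rate > 0.20) ≥ 0.80.

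- n = 10: 0.895 at r = 4, 0.720 at r = 3
- n = 20: 0.826 at r = 6, 0.666 at r = 5
- n = 30: 0.885 at r = 9, 0.783 at r = 8

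The stated boundaries are confirmed.

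**2. Pause probabilities, exact binomial.** By n = 10: P(X₁₀ ≥ 4). The look at 20 adds Σ over x = 0 to 3 of P(X₁₀ = x) × P(Y₁₀ ≥ 6 − x), where Y₁₀ is the count in the next ten. The look at 30 follows in the same way. At a true rate of 0.20: 0.1209 + 0.1109 + 0.0262 = 0.2579.

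| True rate | By n = 10 | By n = 20 | By n = 30 | Plan's Table 10 |
|---|---|---|---|---|
| 0.10 | 1.3% | 2.0% | 2.1% | 2.1% |
| 0.15 | 5.0% | 9.1% | 9.7% | 9.7% |
| 0.20 | 12.1% | 23.2% | 25.8% | 25.8% |
| 0.25 | 22.4% | 42.2% | 47.7% | 47.7% |
| 0.30 | 35.0% | 61.6% | 69.2% | 69.2% |

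Table 10 is reproduced. The issue is the rule's scope, not its arithmetic.

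**3. How many subjects could be affected.** Inputs from SAP 2.3: a ceiling of 46 subjects overall; for the run-in, "Approximately 6 to 12 subjects will be enrolled during the safety run-in portion of the study" (up to 6 at the first level, 6 more at the second); for the two later parts together, "Approximately 34 to 40 subjects will be enrolled for dose optimization and dose expansion"; and for the chosen dose, "It's anticipated that approximately 20 to 40 subjects will be treated at the final expansion dose". With a 12-subject run-in, 6 per level, and F subjects at the final dose, optimization subjects at the other dose number 46 − F − 6:

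- F = 20: 20
- F = 30: 10
- F = 40: 0

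If the run-in were only 6 subjects, split 3 and 3 (an assumption), the figures would be 23, 13 and 3. Optimization subjects at the dose later selected would add to these. Their number cannot be derived, because no size is given for optimization alone.

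**4. What a look could prevent.** Take the F = 20 case. If only the 20 optimization subjects are counted, the look at 10 leaves 10 still to enroll and the look at 20 leaves none. If run-in subjects at that level are counted as well, the level holds 26, so the looks at 10 and 20 leave 16 and 6.

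**5. Cost of running the rule at two levels**, assuming independence. With looks at 10 and 20 at one level and at 10 only at the other, the chance of at least one pause at a true rate of 0.20 is 1 − (1 − 0.232)(1 − 0.121) = 0.32. With both looks at both levels it is 1 − (1 − 0.232)² = 0.41. At a true rate of 0.10 the same sums give 1 − 0.980 × 0.987 = 0.03 and 1 − 0.980² = 0.04.

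**The case against.** Several objections have weight, and each rules out a stronger reading.

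- **A reader might infer that these subjects are unmonitored.** They are not. Under Protocol 8.3.6.2 the internal safety committee reviews data about every 3 months, may review ad hoc and may recommend changes. Protocol 7.1 and Tables 6 and 7 act on individual subjects. Nor can one say that the committees have no boundary, because their charters are not among the documents. The claim is limited to what the protocol and SAP state.
- **A reader might infer that 20 or more subjects will be exposed.** That needs the bottom of the 20-to-40 range for the final dose and every remaining subject at the other dose. Optimization is optional, and the sponsor may go straight to expansion. The number could be zero.
- **A reader might quote the n = 20 probabilities as protection lost.** Where only 20 optimization subjects are counted, a pause at the twentieth spares nobody. The n = 10 figures are the relevant ones there.
- **A reader might say that the higher level enters optimization on run-in data alone.** Protocol 2.2.1.3 reports that the companion Phase 1b study cleared all its dose levels. Section 2.1.3 gives early data on 27 subjects with a median follow-up of 5.8 months, well beyond Cycle 1.
- **A reader might infer that a dose past the boundary would slip into expansion.** The dose is chosen on the totality of data from both studies, so those events would be in view. The documents do not say whether earlier subjects at the selected dose count toward Table 9.

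What remains is the scope gap. None of these safeguards, as the two documents describe them, supplies an aggregate numeric trigger during optimization, and neither document explains why one is needed only after the dose is chosen.

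**Conclusion.** The gap is real and explicit in both documents, and closing it is a cheap improvement rather than the repair of a serious defect. Under SAP figures with a 12-subject run-in, it concerns up to 20 subjects at the non-selected dose, 10 in the middle of the range and about none at the top. For a level with a true Grade 4+ related rate of 0.30, the sponsor's own boundaries would give a 35.0% chance of a pause by 10 subjects and 61.6% by 20; the present text gives no numeric trigger. These probabilities assume independent subjects with a constant event rate, and they ignore the level's having already passed the run-in DLT rule.

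**What to change.** Change the scope sentence in Protocol 9.4.2 and SAP 7.7 so that the existing boundaries apply from completion of the safety run-in, through dose optimization and dose expansion, separately for each combination dose level and cumulatively over everyone treated at that level, run-in subjects included. State that crossing a boundary pauses enrollment at that level for review. The threshold, prior, boundaries and the three permitted actions after a pause stay as they are. This also settles who counts toward Table 9.

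Do not state that Table 10 holds for each level. It describes one stream with a maximum of 40, and two levels sharing 46 subjects cannot both reach that. Label it, and the 40 row of Table 9, accordingly. Add the by-10 and by-20 columns from the working for smaller levels.

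The cost is a short text change, relabelled tables and some extra pauses. With two levels running, the chance of at least one pause is about 3–4% at a true rate of 0.10 and 32–41% at 0.20. Continuing without changes remains one of the permitted outcomes.

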9.4.3. Pharmacokinetic Analyses

Concentrations of RMC-4630 and sotorasib will be summarized descriptively by timepoint. Concentrations of RMC-4630 may be used for population PK analysis and presented in a separate report.

9.4.4. Other Analyses

Additional efficacy and biomarker exploratory analyses will be described in the Statistical Analysis Plan (SAP) finalized before database lock.

APPENDIX 1. REGULATORY, ETHICAL, AND STUDY OVERSIGHT CONSIDERATIONS

Regulatory and Ethical Considerations

- This study will be conducted in accordance with the protocol and with the following:
 - Consensus ethical principles derived from international guidelines including the Declaration of Helsinki and Council for International Organizations of Medical Sciences (CIOMS) International Ethical Guidelines
 - Applicable International Council for Harmonisation of Technical Requirements for Pharmaceuticals for Human Use (ICH) Good Clinical Practice (GCP) guidelines
 - Applicable laws and regulations
- The protocol, protocol amendments, informed consent form (ICF), current RMC-4630 Investigator's Brochure (IB), and other relevant documents (eg, subject information, advertisements) must be submitted to an Institutional Review Board (IRB)/Independent Ethics Committee (IEC) by the investigator and reviewed and approved by the IRB/IEC before the study is initiated.
- Any amendments to the protocol will require IRB/IEC approval before implementation of changes made to the study design, except for changes necessary to eliminate an immediate hazard to study subjects.
- The investigator will be responsible for the following:
 - Providing written summaries of the status of the study to the IRB/IEC annually or more frequently in accordance with the requirements, policies, and procedures established by the IRB/IEC
 - Notifying the IRB/IEC of serious adverse events or other significant safety findings as required by IRB/IEC procedures
 - Providing oversight of the conduct of the study at the site and adherence to requirements of 21 Code of Federal Regulation (CFR), ICH guidelines, the IRB/IEC, and all other applicable local regulations

Financial Disclosure

Investigators and sub investigators will provide the Sponsor with sufficient, accurate financial information as requested to allow the Sponsor to submit complete and accurate financial certification or disclosure statements to the appropriate regulatory authorities. Investigators are responsible for providing information on financial interests during the study and for 1 year after study completion.

Informed Consent Process

- The investigator or his/her designated representative will explain the nature of the study to the subject and answer all questions regarding the study.

- Subjects must be informed that their participation is voluntary. Subjects will be required to sign a statement of informed consent that meets the requirements of 21 CFR 50, local regulations, ICH guidelines, Health Insurance Portability and Accountability Act (HIPAA) requirements, where applicable, and the IRB/IEC or study center.
- The medical record must include a statement that written informed consent was obtained before the subject was enrolled in the study and the date the written consent was obtained. The authorized person obtaining the informed consent must also sign the ICF.
- Per IRB/IEC requirements, subjects must be reconsented to the most current version of the ICF(s) during their participation in the study.
- A copy of the ICF(s) must be provided to the subject.

Subjects who are re-screened are not required to be re-consented; all re-screening should occur within 5 days of the initial date of the screen failure (see [Section 5.4](#))

The investigator or authorized designee will explain to each subject the objectives of the exploratory research. Any remaining mandatory samples may be used for optional exploratory research. Subjects will be told that they are free to refuse to participate and may withdraw their consent at any time and for any reason during the storage period.

Data Protection

- Subjects will be assigned a unique identifier by the Sponsor. Any subject records or datasets that are transferred to the Sponsor will contain the identifier only; subject names or any information which would make the subject identifiable will not be transferred.
- The subject must be informed that his/her personal study related data will be used by the Sponsor in accordance with local data protection law. The level of disclosure must also be explained to the subject.
- The subject must be informed that his/her medical records may be examined by Clinical Quality Assurance auditors or other authorized personnel appointed by the Sponsor, by appropriate IRB/IEC members, and by inspectors from regulatory authorities.

Dissemination of Clinical Study Data

- The posting of company Sponsored clinical trial information and tabular study results on the United States (US) National Institute of Health (NIH) website (www.clinicaltrials.gov) and on other regional clinical trial registries in countries or regions where the clinical trial is conducted, will comply with local regulations.
- Periodic safety reports will be submitted as required by regulation in the countries where the study is conducted.

Data Quality Assurance

- All subject data relating to the study will be recorded on electronic Case Report Form (eCRF) unless transmitted to the Sponsor or designee electronically (eg, laboratory data). The investigator is responsible for verifying that data entries are accurate and correct by physically or electronically signing the Case Report Form (CRF).
- The investigator must maintain accurate documentation (source data) that supports the information entered in the CRF.
- The investigator must permit study related monitoring, audits, IRB/IEC review, and regulatory agency inspections and provide direct access to source data documents.
- Monitoring details describing methods, responsibilities, and requirements, including handling of noncompliance issues and monitoring techniques (central, remote, or onsite monitoring) are provided in the Monitoring Plan.
- The Sponsor or designee is responsible for the data management of this study including quality checking of the data.
- The Sponsor assumes accountability for actions delegated to other individuals (eg, contract research organizations [CROs]).
- Study monitors will perform ongoing source data verification to confirm that data entered into the CRF by authorized site personnel are accurate, complete, and verifiable from source documents; that the safety and rights of subjects are being protected; and that the study is being conducted in accordance with the currently approved protocol and any other study agreements, ICH GCP, and all applicable regulatory requirements.
- Records and documents, including signed ICFs, pertaining to the conduct of this study must be retained by the investigator for a period of 2 years following the date a marketing application is approved for RMC-4630 for the indication for which it is being investigated; or if no application is to be filed or if the application is not approved for such indication, until 2 years after the investigation is discontinued and US Food and Drug Administration (FDA) is notified (ie, in accordance with 21 CFR 312.62(c), unless local regulations or institutional policies require a longer retention period). No records may be destroyed during the retention period without the written approval of the Sponsor. No records may be transferred to another location or party without written notification to the Sponsor.

Source Documents

- Source documents provide evidence for the existence of the subject and substantiate the integrity of the collected data. Source documents are filed at the investigator's site.
- Data entered on the CRF or entered in the eCRF that are transcribed from source documents must be consistent with the source documents or the discrepancies must be explained. The investigator may need to request previous medical records or transfer records, depending on the study. Also, current medical records must be available.

Study and Site Closures

The Sponsor reserves the right to close the study site or terminate the study at any time for any reason at the sole discretion of the Sponsor. Study sites will be closed upon study completion. A study site is considered closed when all required documents and study supplies have been collected and a study site closure visit has been performed.

The investigator may initiate study site closure at any time, provided there is reasonable cause and sufficient notice is given in advance of the intended termination.

Reasons for the early closure of a study site by the Sponsor or investigator may include but are not limited to:

- Failure of the investigator to comply with the protocol, the requirements of the IRB/IEC or local health authorities, the Sponsor's procedures, or GCP guidelines
- Inadequate recruitment of subjects by the investigator
- Discontinuation of further study treatment development

Publication Policy

- The Sponsor will comply with the requirements for publication of study results, and the results of this study may be published or presented at scientific meetings. In accordance with standard editorial and ethical practice, the Sponsor will generally support publication of multicenter studies only in their entirety and not as individual site data. In this case, a coordinating investigator will be designated by mutual agreement. The coordinating investigator agrees to submit all manuscripts or abstracts to the Sponsor before submission. This allows the Sponsor to protect proprietary information and to provide comments.
- Authorship will be determined by mutual agreement and in line with International Committee of Medical Journal Editors (ICMJE) authorship requirements.

